
 • To explore the effect of C21 versus placebo as add on to SoC on inflammation. 	
 • Change from baseline in CRP at Day 15.

 • To explore the effect of C21 versus placebo as add on to SoC on lung injury. 	
 • Change from baseline in lactate dehydrogenase (LDH) at Day 15.

Primary estimand

All-cause mortality up to Day 60 defined as the time to day of death from any cause assessed for the intention-to-treat population with treatment as randomized, independent of treatment withdrawal or major protocol deviations according to the treatment policy, with subjects with no confirmed death before or at Day 60 being censored at day of withdrawal/Day 60 follow-up. The stratified log-rank test will be used to compare the treatments. The treatment difference will be expressed as a hazard ratio with 95% confidence intervals.

Key Secondary estimands

Time to sustained hospital discharge up to Day 60; The first occurrence of a score ≤ 2 whereafter the score stays ≤ 2 for the remainder of the 60 days trial period, assessed for the intention-to-treat population with treatment as randomized, independent of treatment withdrawal or major protocol deviations according to the treatment policy, with subjects who die prior to Day 60 being censored at Day 60 and subjects withdrawing due to other causes than death and not fulfilling the event being censored at the withdrawal day. The Kaplan-Meier difference in median time to sustained hospital discharge with 95% confidence intervals will be estimated.

Supplemental oxygen free days up to Day 29; For each subject the number of days between Day 1 and Day 29 with a score of ≤ 4 on the 8-point ordinal scale and with no documented use of COVID-19 related supplemental oxygen, assessed for the intention-to-treat population with treatment as randomized, independent of treatment withdrawal or major protocol deviations according to the treatment policy, with subjects who die prior to Day 29 being given the value -1 day and trial withdrawals prior to Day 29 due to other causes than death and not possible to follow-up being imputed using multiple imputation including assessments from day 1 to day 29. The Hodge-Lehmann median estimated of the difference in days between treatments with 95% confidence intervals will be estimated.

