Proportion of subjects free of respiratory failure at Day 15; The proportion of subjects with a score of ≤ 5 on the 8-point ordinal scale at Day 15, assessed for the intention-to-treat population with treatment as randomized, independent of treatment withdrawal or major protocol deviations according to the treatment policy, with subjects who die prior to Day 15 considered as respiratory failure and trial withdrawals prior to Day 15 due to other causes than death and not possible to follow-up being imputed using multiple imputation including their baseline characteristics and last known status. The difference in proportions between treatments with 95% confidence intervals will be estimated.

Proportion of subjects discharged from hospital and free of supplemental oxygen at Day 15; The proportion of subjects with a score of ≤ 2 on the 8-point ordinal scale and free of COVID-19 related supplemental oxygen use at Day 15, assessed for the intention-to-treat population with treatment as randomized, independent of treatment withdrawal or major protocol deviations according to the treatment policy, with subjects who die prior to Day 15 considered not discharged and trial withdrawals prior to Day 15 due to other causes than death and not possible to follow-up being imputed using multiple imputation including baseline characteristics and their last known status. The difference in proportions between treatments with 95% confidence intervals will be estimated.

4. Trial Design

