8.2. Efficacy Assessments

Planned timepoints for all efficacy assessments are provided in the SoA.

8.2.1. 8-point Ordinal Scale

The clinical status of COVID-19 is scored at each visit according to the 8-point ordinal scale ([Beigel et al., 2020](#)), which is an investigator evaluation of the clinical status at the first assessment of a given trial day. The clinical status of COVID-19 according to the 8-point ordinal scale must further be scored at the time of hospital discharge. For subjects hospitalized between Day 29 (Visit 31) and Day 60 (Visit 32), the clinical status of COVID-19 should be scored each time a change in clinical COVID-19 status is seen and until hospital discharge.

The 8-point ordinal scale is as follows:

1.	Not hospitalized, no limitations on activities
2.	Not hospitalized, limitation on activities and/or requiring home oxygen
3.	Hospitalized, not requiring supplemental oxygen - no longer requires ongoing medical care
4.	Hospitalized, not requiring supplemental oxygen - requiring ongoing medical care (COVID-19-related or otherwise)
5.	Hospitalized, requiring supplemental oxygen
6.	Hospitalized, on non-invasive ventilation or high flow oxygen devices
7.	Hospitalized, on invasive mechanical ventilation or ECMO
8.	Death

A subject re-admitted to the hospital for a non-COVID-19 related reason should be considered not hospitalized when scoring the clinical status of COVID-19 on the 8-point ordinal scale.

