The second key secondary endpoint, oxygen supplemental free days up to Day 29, will be defined as the number days for each subject with a score of ≤ 4 and no use of COVID-19 related supplemental oxygen. Treatment groups will be compared using the Wilcoxon rank-sum test and the treatment difference will be expressed as the Hodge-Lehmann difference in median number of days with 95% confidence intervals. All collected data post-treatment will be used. Subjects who die prior to Day 29 will be given the value of -1 day in the analysis and trial withdrawals prior to Day 29 due to other causes of death will be imputed (for each day) using multiple imputation including status for all of days 1 - 29. The cumulative distribution functions will be plotted to visualize the differences between treatment groups.

The third key secondary endpoint, subjects free of respiratory failure, will be defined as subjects with an ordinal scale score of ≤ 5 at Day 15. Treatment groups will be compared using a logistic regression model adjusting for treatment, baseline disease severity and region. All collected data post-treatment will be used to assess the scores. Subjects who die prior to Day 15 will be considered in respiratory failure and trial withdrawals prior to Day 15 due to other causes than death and not possible to follow-up will be imputed using multiple imputation taking subjects

baseline characteristics and last known status into account. The adjusted proportions as calculated from ([Ge et al., 2011](#)) and the statistics (treatment difference, SE and CI) following multiple imputation will also be presented. The ITT will be used for the analysis. The number of responders/non-responders will also be presented (these will be the non-imputed values).

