10.5 Prior and Concomitant Therapy

Prior therapies are defined as those with a start date prior to the first dose of IMP.

Therapies which start prior to the first dose of IMP and are ongoing at the time of first dose of IMP will be summarized as both prior and concomitant therapies.

Concomitant therapies are defined as those started prior to but continuing after randomization or with a start date on or after randomization. For therapies that start prior to but ended on randomization date they will be considered prior therapies only.

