10.10 Supplemental Oxygen Use

Hospitalized subjects will be assessed on a daily basis for their oxygen use. If a subject is discharged, they may be prescribed supplemental oxygen for at-home use. On each visit following discharge a subject will be assessed if they have used oxygen since the last visit and which days and if they have used supplemental oxygen this will be recorded on the concomitant medication page of the CRF. Subjects who have used supplemental oxygen since the previous visit will also be assessed if they are still on oxygen at the visit.

If a subject has a scheduled ordinal scale score of 1, 3, or 4 (i.e. free of supplemental oxygen use) and there is evidence of supplemental oxygen usage, the value on the adjusted ordinal scale will not be changed and the investigator's judgement will be considered the most accurate assessment of clinical status. The collected ordinal scale value will be used as the value in the analysis and the subject will be considered free of supplement oxygen usage on the trial day of interest.

For discharged subjects, the daily oxygen use will be derived. If a subject has oxygen use on a trial day they will be assigned a value of 2 on the adjusted 8-point ordinal scale on the trial days between the oxygen start and end day. A discharged subject will be considered to be using supplemental oxygen on a trial day if:

1. The subject has a record at the time point for supplemental oxygen use on the Oxygen supplementation during oxygen saturation measurement page of the CRF.
2. The subject has "Yes" at a time point to the question "Was subject still on COVID-19 related supplemental oxygen at the time of visit" on the Visit page of the CRF for discharged subjects at Day 8, Day 22, Day 29 and Day 60 and on the End of Treatment page for Day 15.
3. If a subject has a missing ordinal scale score on the day of discharge or a value of 2 on the ordinal scale and on the Hospitalization CRF page the question "Was COVID-19 related supplemental oxygen for at home use prescribed?" is Yes then a subject will be considered on supplemental oxygen at discharge and the visit that corresponds with discharge.
4. Subject has a record on the concomitant medication page for post-baseline supplemental oxygen use (preferred term entered as Oxygen and the therapy is concomitant per Section 10.5)

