12.5.3.2 Time to Sustained Hospital Discharge

Time to sustained hospital discharge, will be defined as time to discharge after which no re-hospitalizations due to COVID-19 occur. Please refer to Section 10.12 for further details on this calculation.

Treatment groups will be compared using a stratified log-rank test adjusting for treatment, actual baseline disease severity and region. The size of the treatment effect will be estimated as a hazard ratio, obtained using a Cox proportional hazards regression model and the Cox regression model will include a factor for

randomized treatment, baseline disease severity and region. The estimated hazard ratios for each treatment group will be presented together with the corresponding 95% CI (based on Wald test).

Analysis will be illustrated using a Kaplan-Meier plot and the median time to hospital discharge will be estimated with 95% CIs for each treatment group. Subjects who die prior to Day 60 will be censored at Day 60 and trial withdrawals prior to Day 60 due to other causes than death without fulfilling the event will be censored at day of withdrawal. Subjects still in trial but not discharged from hospital at Day 60 will be censored at their Day 60 trial visit.

12.5.3.3 Oxygen Supplemental Free Days up to Day 29

Oxygen supplemental free days up to Day 29 will be defined as the number days for each subject with a score of ≤ 4 and no use of COVID-19 related supplemental oxygen. Refer to Section 10.13 for the derivation of number of oxygen free days.

Subjects who die prior to Day 29 will be given a value of -1 days in the analysis. Subjects who withdraw from the trial prior to Day 29 and have missing data will have their data multiply imputed as per Section 10.19.1. Subjects who chronically used supplemental oxygen prior to their COVID-19 illness will be considered oxygen free when they return to the same level of oxygen support they had been using prior to COVID-19.

Treatment groups will be compared using the Wilcoxon rank-sum test (using p-values) and the treatment difference will be expressed as the Hodges-Lehmann difference in median number of days with 95% CIs. All collected data post treatment will be used. Summary statistics for the number of oxygen free days will also be presented for each treatment group. A cumulative distribution plot of the number of oxygen free days by treatment arm will also be produced.

12.5.3.4 Subjects Free of Respiratory Failure at Day 15

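### For discharged subjects, SAP 10.10 counts oxygen of any cause, whereas the estimands for oxygen-free days and the Day 15 discharge endpoint exclude only COVID-19 related oxygen; the chronic-user rule of SAP 12.5.3.3 is also missing from the derivations

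*SAP*

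**What the plan says.** **Estimands.** Protocol Section 3 defines oxygen-free days as days with a score of 4 or less and "with no documented use of COVID-19 related supplemental oxygen". It defines the Day 15 responder as a subject with a score of 2 or less who is "free of COVID-19 related supplemental oxygen use at Day 15". Protocol 9.3.3 repeats both; for oxygen-free days its condition is "no use of COVID-19 related supplemental oxygen". SAP Appendix 1 carries the same restriction for both endpoints, and SAP 12.5.3.3 carries it for oxygen-free days.

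**Derivation.** SAP 10.10 lists four sources, any one of which puts a discharged subject on oxygen for a trial day:

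- Item 1: a record on the oxygen page that accompanies the saturation measurement. It has no cause filter.
- Item 2: a visit question limited to COVID-19: "Was subject still on COVID-19 related supplemental oxygen at the time of visit".
- Item 3: home oxygen prescribed at discharge, also limited to COVID-19.
- Item 4: "Subject has a record on the concomitant medication page for post-baseline supplemental oxygen use (preferred term entered as Oxygen". It has no cause filter.

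Item 4 relies on SAP 10.5: "Concomitant therapies are defined as those started prior to but continuing after randomization". Long-term home oxygen therefore qualifies.

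According to SAP 10.19.1 step 3 and Appendix 5, only adjusted scores 1, 3 and 4 count as oxygen-free days, and only adjusted score 1 is a Day 15 response. A discharged subject scored 2 with any qualifying oxygen record stays at 2 and fails both.

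**Chronic users.** SAP 12.5.3.3 adds: "Subjects who chronically used supplemental oxygen prior to their COVID-19 illness will be considered oxygen free when they return to the same level" of support as before. That rule appears nowhere else in the SAP.

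**The concern.** A programmer who follows SAP 10.10 and Appendix 5 exactly will produce a variable that differs, for some subjects, from the one in the SAP's own estimand table. Within 10.10, a No to the COVID-19 specific visit question can be overridden by an unrelated entry on the concomitant medication page. For chronic users, SAP 12.5.3.3 and the derivation sections give different day counts for the same person.

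These endpoints stand third and fifth in the testing hierarchy, so each may carry a confirmatory claim if the earlier tests succeed. If the texts are not reconciled while the trial is blinded, someone must choose between two written definitions later, possibly with results in view. The planned sensitivity analyses would not show the consequence. The per-protocol and ANOVA analyses keep the same oxygen rule, and the tipping-point and worst-case analyses are built on the same adjusted score.

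**Working it through.** The plan gives no figure to reproduce. The check sets the two definitions side by side for individual subjects.

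**Where the definitions part.** SAP 10.10 keeps a scheduled score of 1, 3 or 4 even when oxygen is recorded. A conflict therefore needs a discharged day, an oxygen record not related to COVID-19, and no scheduled score of 1. That covers days between visits and visits scored 2, Day 15 included. COVID-19 related oxygen is treated alike under both texts.

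**Example 1: chronic user.** Assume discharge on Day 6 to the usual oxygen, an open oxygen entry on the concomitant medication page, and post-discharge visits on Days 8, 15, 22 and 29 (SAP 10.9).

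| Rule | Oxygen-free days |
|---|---|
| SAP 12.5.3.3, Days 7 to 29 | 29 − 7 + 1 = 23 |
| Derivation, scored 2 at visits | 0 |
| Derivation, scored 1 at visits | 4 (Days 8, 15, 22, 29) |

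The last row is less likely, because score 2 is the category that names home oxygen.

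**Example 2: non-COVID re-admission.** Assume a discharged subject is re-admitted on Days 13 to 16 for another reason, with oxygen on the concomitant medication page and a Day 15 score of 2. SAP 10.8 scores such a subject as not hospitalized.

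- Estimands: 16 − 13 + 1 = 4 oxygen-free days over that stay, and a Day 15 responder.
- SAP 10.10 item 4 with Appendix 5: adjusted score 2 throughout, so 0 days and a non-responder.

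**Trial level.** With the maximum of 150 subjects per arm, one reclassified subject moves an arm's crude Day 15 proportion by 1/150 = 0.67 percentage points. The documents do not say how many subjects are affected. If, purely as an assumption, one arm has 0 to 3 more such subjects than the other, the difference moves by 0 to 3/150 = 2.0 points. On the mean scale, one chronic user as in example 1 (scored 2) shifts an arm by 23/150 = 0.15 days, and 0 to 3 such subjects by 0 to 3 × 23/150 = 0.46 days. The mean figures are illustrative only, because the main analysis is a Wilcoxon test with a Hodges-Lehmann estimate.

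**Is the departure declared?** SAP 6.1 lists changes from the protocol, including a derivation-level change to time to sustained discharge. It does not list the any-cause oxygen rule.

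**The case against.** The strongest reply is that any-cause counting was a deliberate choice made without unblinded data. The version 1.5 entry in the SAP change history says that all concomitant oxygen counts whatever the reason, which agrees with item 4 as it now stands. Such a rule applies equally to both arms and avoids judging attribution. The endpoint titles, SAP 10.8 and SAP 12.5.3.5 carry no cause restriction either. This stands as a defence of the rule. It does not reconcile the rule with Appendix 1 and 12.5.3.3, which still say otherwise.

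On chronic users, it can be said that 12.5.3.3 states a specific exception to be read with the general derivation, and that 10.19.1 step 3 refers back to 12.5.3.3. That is a fair reading of intent. But 12.5.3.3 sends the reader to 10.13 for the count, and neither 10.13 nor the sum in Appendix 5 can reproduce the exception.

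A reader might infer more than the documents support:

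- That SAP 6.1 should also list the chronic-user omission. The protocol's estimand and analysis text has no such rule, so this is a matter internal to the SAP.
- That a chronic user back at the usual level in hospital must score 5 ("Hospitalized, requiring supplemental oxygen") and so fail the score condition. The scale is an investigator's rating of COVID-19 status, and no text says how usual oxygen is scored in hospital.
- That the chronic-user rule governs Day 15. It is written only for oxygen-free days; the Day 15 mismatch rests on the COVID-19 related wording alone.
- That item 1 has wide reach. SAP 10.18 says discharged subjects have no site assessments, while the protocol brings them to the clinic on Day 15, so its reach is uncertain.
- That letting a scheduled score of 1, 3 or 4 prevail over an oxygen record is an error. It is a prespecified source hierarchy.

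**Conclusion.** The conflict is in the current text and should be fixed. For two alpha-controlled key secondary endpoints, the derivation for discharged subjects counts oxygen that the estimands disregard, and SAP 6.1 does not declare this departure. The chronic-user rule is stated once and carried into no derivation.

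For one subject the gap can be large: 23 days against 0, or responder against non-responder. For the trial it is probably small. The number affected is unknown, the 0 to 2.0 point range rests on an assumed imbalance of up to three subjects, and the primary mortality analysis does not use the oxygen definition. It does not follow that any-cause counting is the wrong choice, or that the endpoints are mis-measured throughout. The firm requirement is that the texts agree.

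**What to change.** Before unblinding, make derivation and estimand agree in one of two ways:

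- **Restrict the derivation.** Limit item 4 of SAP 10.10 to COVID-19 related oxygen using the recorded reason for use (Protocol 6.8), and disregard an item 1 record where the concomitant record gives another reason.
- **Keep the any-cause rule.** Amend Appendix 1 and 12.5.3.3, list the departure in 6.1, and run the COVID-19 related version as a sensitivity analysis.

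In either case, write the chronic-user rule into 10.10, 10.13, 10.19.1 step 3 and Appendix 5, mapping affected discharged days to adjusted score 1. Identify these subjects from the chronic oxygen history (Protocol 8.1.2). State whether the rule applies in hospital and whether it applies at Day 15. Settle unclear cases at the blinded data review (SAP Appendix 4).

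The cost is SAP wording and some derivation code. Reason for use and chronic oxygen history are already collected. A pre-COVID flow rate may not be, so matching to the earlier level may be approximate. Some adjusted scores entering the multiple imputation would change from 2 to 1; the model form would not.

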10.11 All-Cause Mortality

All-cause mortality is defined as time to day of death from any cause during the study. Time to all-cause mortality will be defined as:

$$\text{Time to all cause mortality (days)} = \text{Date of Death or Censor} - \text{Date of first dose of IMP} + 1$$

where the date of death will correspond to the date of death recorded in the CRF. Subjects without the event will be censored at day of withdrawal/Day 60 follow-up date in this analysis. If a subject is indicated to have died in the data, but date of death is missing, the last available date for the subject in the database will be used as the day of death.

10.12 Time to Sustained Hospital Discharge

Time to sustained hospital discharge is defined as the time to the date of discharge from initial hospitalization or re-hospitalization due to COVID-19 after which the subject is not re-hospitalized for COVID-19 related reasons.

If a subject dies, they will be censored at Day 60, if a subject withdraws (for reasons other than death) from the trial prior to observing the event (i.e. while still hospitalized) they will be censored at the time of withdrawal. If a subject has an event and subsequently withdraws (for reasons other than death), they will be treated as having the event in the analysis. Subjects who complete the trial without the event i.e. are still hospitalized at Day 60, will be censored at Day 60 in the analysis.

The calculation will be as follows:

$$\text{Time to sustained discharge (Days)} = \text{Date of Event or Censor} - \text{Date of first dose of IMP} + 1$$

where date of event for subjects who discharge will be the date of discharge from hospital (after which the subject is not re-hospitalized for COVID-19 reasons) as recorded on the Hospitalization CRF page. If a subject is re-hospitalized for COVID-19 reasons, the date of event will be the end date of this re-hospitalization (if no subsequent re-hospitalization for COVID-19 reasons).

Additionally, a sensitivity analysis will be performed where all re-hospitalizations are considered as COVID-19 related regardless of the investigator indicated cause. In the sensitivity analysis, date of event for subjects with missing data and no discharge record on the hospitalization form will be the relative day a value of ≤ 2 is achieved after which a subject has only imputed values of ≤ 2 for all subsequent visits. If subjects with imputed data have a recorded value of discharge on the hospitalization page and imputed data is ≤ 2 from this date of discharge, the recorded date of discharge will be used as event date in the calculation. If subjects with imputed data have a recorded value of discharge on the hospitalization page and any imputed data is > 2 from this date of discharge, time to sustained discharge will be the relative day a value of ≤ 2 is achieved after which a subject has an imputed value of ≤ 2 for all subsequent visits. If a subject with imputed data never observes the event they will be censored at Day 60.

